#### 8.1.4 Pruritus Numeric Rating Scale

The intensity of pruritus will be recorded at the visits specified in Section 7 using a Pruritus Numeric Rating Scale (15). This will be evaluated by asking subjects to assign a numerical score representing the current intensity of their symptoms over the last 24h on a scale from 0 to 10, with 0 for having no symptoms and 10 having worst imaginable symptoms. The NRS of pruritus is provided in APPENDIX B.

## **8.2 Quality-of-Life Assessments**

#### 8.2.1 Dermatology Life Quality Index Questionnaire

The Dermatology Life Quality Index (DLQI) is a simple 10-question validated questionnaire that has been used in more than 40 different skin conditions. Its use has been described in more than 1,000 publications, including many multinational studies. The DLQI is the most frequently used instrument in studies of randomized controlled trials in dermatology. It will be completed at the visits specified in Section 7. The questionnaire is provided in APPENDIX C.

## **8.3 Safety Assessments**

#### 8.3.1 Vital Signs

The following vital signs will be recorded at every visit with the subject in a seated position, after having sat calmly for at least 5 minutes: systolic and diastolic blood pressure (mmHg), pulse (bpm), and body temperature (°C).

Weight (kg) and height (cm) will be collected to calculate the Body Mass Index (BMI) which will be recorded at the screening and baseline (Day 0) visits. The height will only be recorded once at the screening visit and the same value will be used for BMI calculation at baseline (Day 0). The weight will be recorded at screening, baseline (Day 0), and at the Week 12 visit (end of treatment visit).

If deemed appropriate by the investigator, clinically significant findings in the vital signs will exclude a subject from study participation. Any abnormal finding related to vital signs that the investigator considers to be clinically significant must be recorded as an AE if this abnormality was not present at the baseline (Day 0) visit or is assessed as having worsened since baseline (Day 0). Any change in health between the informed consent form and the first study drug administration will be recorded as medical history.

#### 8.3.2 Physical Examination

The following sites/systems will be included in the physical examination to be performed at the visits specified in Section 7. In case clinically significant findings are detected at Week 12, the physical examination may be repeated at Week 16. Each system will be scored as normal/abnormal

(nonclinically significant or clinically significant). Pertinent details must be recorded for any clinically significant findings.

- General appearance
- Dermatological (except psoriasis)
- Head, eyes, ears, nose, throat (HEENT)
- Respiratory
- Cardiovascular
- Abdominal
- Neurological
- Musculoskeletal
- Lymphatic

If deemed appropriate by the investigator, clinically significant findings in the physical examination will exclude a subject from study participation. Any significant change will be reported as an AE if this abnormality was not present at the baseline (Day 0) visit or is assessed as having worsened since baseline (Day 0). Any change in health between the informed consent form and the first study drug administration will be recorded as medical history.

### 8.3.3 Clinical Laboratory Tests

Laboratory tests will be performed at the visits specified in Section 7. In case clinically significant findings are detected at Week 12, the corresponding laboratory test may be repeated at Week 16. The tests will include hematology with differential and a standard chemistry panel (chemistry includes liver function tests). A serum pregnancy test will be performed at screening, and a urine pregnancy test will be performed at all the other study visits for women of childbearing potential. In addition, serology testing (HBV, HCV, HIV) and tuberculosis test (PPD, T-spot test or Quantiferon Gold, if one has not been performed in the last 6 months) will be performed at the screening visit only.

All routine laboratory tests will be analyzed at the local laboratory of each trial site.

The specific tests in these panels are listed in Table 3:

**Table 3: Clinical Laboratory Testing**

Laboratory Testing	Tests Included
Hematology	HCT, Hgb, MCH, MCHC, MCV, MPV, platelets, RBC, WBC and differentials (neutrophils, lymphocytes, monocytes, eosinophils and basophils relative and absolute).
Serum chemistry	Albumin, alkaline phosphatase, ALT, AST, chloride, CK, creatinine (enzymatic), GGT, glucose random, HbA1c, LDH, potassium, sodium, total bilirubin, urea (BUN), uric acid, cholesterol, triglycerides
Pregnancy test	$\beta$ -hCG in serum for females of childbearing potential at screening only and urine pregnancy test at the other visits.
Laboratory tests required at screening only	FSH levels for women greater than 40 and less than 60 years of age who have had a cessation of menses for at least 12 months but less than 24 months. Tuberculosis test (PPD, T-spot test or Quantiferon Gold), and serology (HBV [HBsAg, anti-HBc], HCV, HIV)

ALT = alanine aminotransferase; anti-HBc = anti-hepatitis B core antibodies; AST = aspartate aminotransferase;  $\beta$ -hCG =  $\beta$ -human chorionic gonadotropin; BUN = blood urea nitrogen; CK = creatine kinase; FSH = follicle-stimulating hormone; GGT = gamma-glutamyltransferase; HBsAg = hepatitis B surface antigens; HBV = hepatitis B virus; HCT = hematocrit; HCV = hepatitis C virus; Hgb = hemoglobin; HIV = human immunodeficiency virus; LDH = lactate dehydrogenase; MCH = mean corpuscular hemoglobin; MCHC = mean corpuscular hemoglobin concentration; MCV = mean corpuscular volume; MPV = mean platelet volume; PPD = purified protein derivative; RBC = red blood cell (count); WBC = white blood cell (count).

If deemed appropriate by the investigator and in accordance with the exclusion criteria described in Section 5.2, clinically significant findings in clinical laboratory testing will exclude a subject from study participation. Any significant change will be reported as an AE if this abnormality was not present at the baseline (Day 0) visit or is assessed as having worsened since baseline (Day 0). Any change in health between the informed consent form and the first study drug administration will be recorded as medical history.

#### 8.3.4 *Electrocardiogram*

Twelve-lead ECGs will be performed as a safety assessment at the visits specified in Section 7. In case clinically significant findings are detected at Week 12, the ECG may be repeated at Week 16. Clinically significant findings in the ECG will exclude a subject from study participation (as deemed appropriate by the investigator). Any significant change will be reported as an AE if this abnormality was not present at baseline (Day 0) visit or is assessed as having worsened since baseline (Day 0).

#### 8.3.5 *Chest X-Ray*

In addition to PPD, T-spot test or Quantiferon Gold, a chest x-ray will be performed at screening only (if one has not been performed in the last 6 months) to assess the presence of tuberculosis.

## 8.4 Other Assessments

Refer to the study manual for detailed instructions on tube labeling, sample collection, processing, storage, shipping, and laboratories in charge of the analyses below.

### 8.4.1 Skin Biopsies

All subjects will have two 4.0-mm skin biopsy taken from a nonlesional area at the baseline (Day 0) visit and two 4.0-mm biopsy taken from the target lesion at baseline (Day 0), Week 4, Week 8, and Week 12 visits, for a total of 10 biopsies.

The first half will be used for immunohistochemistry staining and will be proceed in OCT.

The second half will be processed in RNAlater and used for gene expression analysis using reverse transcription polymerase chain reaction (RT-PCR).

The skin will be cleaned, disinfected, and anesthetized before skin biopsies are performed. Sterile gauze will be used to absorb any bleeding. The biopsy sites will be cauterized and sutured if necessary.

### 8.4.2 Medical Photography

Medical photographs of another lesion than the target lesions will be performed at baseline (Day 0) and at all subsequent visits (if no other lesions are present on the body, photographs could be performed on a biopsied lesion). Care will be taken to use the same camera, the same magnification, and the same settings for each photograph at each visit in order to obtain comparable pictures. Medical photography will be taken using a blue background.

Photographs will be identified as follows: study number, subject number, subject initials, visit name, and date. Photographs will be kept as electronic files on site and will be transmitted to the sponsor for review.

### 8.4.3 Status of Psoriatic Arthritis

Subjects suffering from psoriatic arthritis (as reported in the subject's medical history at screening) will be asked at the visits specified in Section 7 if their condition has improved, remained stable, or worsened) since the screening visit.

## **9 ADVERSE EVENTS**

An AE is any untoward medical occurrence in a subject administered a pharmaceutical product, without regard to the possibility of a causal relationship with this treatment.

Investigators are responsible for monitoring the safety of subjects who are participating in this study and for alerting the sponsor of any event that seems unusual, even if this event may be considered an unanticipated benefit to the subject. The investigator is responsible for appropriate medical care of subjects during the study.

The investigator remains responsible for following through with an appropriate health care option for all AEs that are serious or that caused the subject to discontinue before completing the study. The subject should be followed until the event is resolved or stable. Follow-up frequency is left to the discretion of the investigator.

Safety will be evaluated by collecting information on AEs and by accessing data from vital signs, ECGs, physical examinations, and laboratory results.

Prior to subject enrollment, study site personnel will note the occurrence and nature of each subject's medical condition(s) in the appropriate section of the source document and CRF. During the study, site personnel will again note any change in the condition(s) and the occurrence and nature of any AEs.

If a subject experiences an AE at any time after the first dose of the study product, the event will be recorded as an AE in the source document and CRF.

### **9.1 Adverse Event Causality**

The investigator will establish causality of the AE to the experimental treatment. The investigator should take into account the subject's history, most recent physical examination findings, and concomitant medications.

The following definitions will be used to determine causality of an AE:

- Not related: Temporal relationship of the onset of the AE, relative to the experimental treatment, is not reasonable, or another cause can explain the occurrence of the AE.
- Related: Temporal relationship of the onset of the AE, relative to the experimental treatment, is reasonable, follows a known response pattern to the treatment, and an alternative cause is unlikely.

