*second-line therapy of patients with Stage IIIb or IV Non-small Cell Lung Cancer - the HALO study (HSP90 inhibition And Lung cancer Outcomes)*, during Part A. It is important to highlight that this study was completed in patients with advanced cancers, specifically Stage IIIb and IV Non-small Cell Lung Cancer (NSCLC), where CUDC-305 administration was being evaluated in combination with cisplatin/pemetrexed and cisplatin/gemcitabine (naive Stage IIIb and IV NSCLC patients) or with docetaxel (previously treated Stage IIIb and IV NSCLC). The proposed trial is designed as a dose-ranging trial in order to explore dose and define the maximum tolerated dose and viable Phase 2 doses in patients with moderate to severe psoriasis (the target population); a unique population that is quite disparate from that of previous trials. Furthermore, discontinuation of the referenced Phase 2 studies were not based on safety concerns and that all safety observations from these studies “were consistent with the previously observed side effects.” Finally, preclinical studies found that CUDC-305 accumulated in dermal tissues versus plasma(11). In a xenograft mouse model of psoriasis daily dosing of CUDC-305 lead to plasma levels of ~2uM and skin levels of ~24 pmol/mg of wet tissue 30 minutes post-dosing on the final treatment day, representing a concentration in skin that exceeds the IC50 (~0.1  $\mu$ M) of CUDC-305 for HSP90 $\alpha/\beta$  (based on the assumption that 1mg of tissue equals 1 ml of biological fluid and taking in to account the 6% unbound plasma fraction of CUDC-305). This suggests that concerns with reduced efficacy being associated with poor oral bioavailability may be less relevant in dermal indications, such as psoriasis.

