#### Safety Endpoints

- Incidence of treatment-emergent adverse events (TEAEs)
- Incidence of related TEAEs

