### **9.3.1 SAE Reporting**

All SAEs, related to the experimental treatment or not, occurring during the course of the study must be reported on an SAE form to the sponsor within 24 hours of the knowledge of the occurrence. (This refers to any AE that meets one or more of the aforementioned serious criteria.) The SAE reporting period ends at the Follow-up visit (Week 16).

Reporting should be done by sending the completed SAE Report Form to the following e-mail address (faxing can also be done as a second option in case e-mailing is not possible).

Contact name: [name]  
Department of Dermatology, Aarhus University Hospital  
[name]  
Denmark  
E-mail: [[contact]](mailto:[contact])  
[contact]  
[contact]

The sponsor will evaluate all SAEs as soon as the reports are received and will assess the expectedness of each SAE in relation to the study treatment. For each SAE received, the sponsor will make a determination as to whether the criteria for expedited reporting to relevant regulatory authorities have been met. The sponsor or designee will manage the expedited reporting of relevant safety information to concerned regulatory agencies in accordance with local laws and regulations.

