### **9.5 Suspected Unexpected Serious Adverse Reactions**

If a subject experience a SUSAR at any time after the first study product administration, the event will be recorded as a SUSAR in the source document and CRF.

SUSARs meets the same criteria as SARs, but are not expected to occur according to the reference safety informations in the Investigator's Brochure.

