### *10.2.3 Safety Analysis*

Safety analysis will be summarized and presented descriptively by evaluating the incidence of TEAEs and drug-related TEAEs.

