patients with moderate-to-severe psoriasis receive systemic treatment(17). This deficiency has been linked to elevated safety concerns(17). Indeed, due to the risk of serious adverse side effects associated with these therapies patients are often required to alternate between various therapeutic modalities as a precautionary measure. Recent publications indicate that oral therapeutics, particularly those without immunosuppressive side-effects, remain a critical unmet need for patients that are unwilling or unable to use injectable treatments(18). Thus, while current guidelines recommend systemic treatment with immunomodulatory biologics(5), in order to achieve adequate disease control in patients with moderate-to-severe psoriasis, efficacious oral psoriasis therapeutics with a strong safety profile that also have a pharmacokinetic profile that permits the management of spontaneously arising adverse effects. The goal of therapy is to bring disease under control by using the least toxic therapy, where drugs associated with risk of serious irreversible toxicity or mortality should be reserved for patients with severe, recalcitrant psoriasis. Potentially serious although reversible gastrointestinal toxicities could be associated with CUDC-305. Although not evident in human studies, preclinical animal data also suggest a potential for an increased QTc intervals in the heart following CUDC-305 and treated patients will be required to undergo mandatory cardiac monitoring. *In vitro* studies suggest that high doses of CUDC-305 may have off-target effects on opioid receptors. Quality of life and study product accountability will be closely monitored. To further mitigate risk during study enrollment all available safety and efficacy data will be reviewed by the principal investigator (PI) or delegate and the sponsor's medical monitor before subsequent cohorts are dosed. A safety meeting will take place to review the available data prior to deciding the next dose and then initiating dosing of the subsequent cohort. The study may be stopped permanently or interrupted at any time for safety reasons following review of study data. If any subject from the sentinel cohort experiences a severe or clinically significant adverse event (AE) that is considered possibly drug-related, then dosing of the remaining cohorts with higher doses will not be conducted. Dose escalation can only proceed if all parties (PI or delegate and the sponsor's medical monitor) agree that it is safe to do so and will be documented in the form of a signed dose decision document. Participants will be closely monitored at all times during the study by experienced medical, nursing and clinical staff. In the event of an unexpected AE or medical emergency the participant will be transferred to a hospital for further management this will be implemented without delay. Phase I clinical studies support a favorable toxicity profile of CUDC-305 and the overall risk:benefit, considering all aspects detailed above, is considered to be acceptable to support commencing the study in patients with moderate to severe psoriasis.

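### Section 9.1 makes a known response pattern a condition for Related, so a novel drug reaction fits neither causality class and the related-TEAE endpoint is undefined for it

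*Protocol*

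**What the plan says.** Protocol Section 9.1 has the investigator assign causality and prescribes two definitions. Not related applies when the timing of onset "is not reasonable, or another cause can explain the occurrence of the AE"; either limb is enough. Related applies when the timing "is reasonable, follows a known response pattern to the treatment, and an alternative cause is unlikely"; the three conditions are joined by *and*. There is no intermediate or unknown class, and no rule for an event that meets neither definition.

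The classification feeds a named endpoint. Section 3.2 lists two safety endpoints, TEAE incidence and "Incidence of related TEAEs". Section 10.2.3 makes the safety analysis descriptive, by "evaluating the incidence of TEAEs and drug-related TEAEs".

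Causality wording also appears in two safety rules. Section 6.2.7 allows suspension after a severe AE or an SAE, with an exception where the investigator finds the event unrelated. Section 15.4 rules out higher doses after a severe or clinically significant event in the sentinel cohort that is thought possibly drug-related.

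**The concern.** The two definitions are not complements. Not related asks about timing and other causes. Related asks about these and adds a third condition, the known pattern, which has no counterpart in Not related. A reaction that the drug truly causes but that nobody has yet associated with it can therefore fall between the two.

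Related-TEAE incidence is one of only two safety endpoints, in a Phase 1b study with safety and tolerability as a secondary objective. An investigator who meets such an event has to choose a class without guidance, and the same event could be filed either way. Filing it as Not related, because the pattern is unknown, lowers the reported incidence for the very events that are new.

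**Working it through.** The protocol states no figure on this point, so there is none to reproduce. The check is logical.

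1. **Terms, from Section 9.1.** T: timing is reasonable. K: there is a known response pattern. C: another cause can explain the event. U: an alternative cause is unlikely.
   - Not related = (not T) or C.
   - Related = T and K and U.

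2. **The gap case.** Take T yes, K no, C no. Related fails on K. Not related fails on both limbs, because timing is reasonable and no other cause can explain the event. This step needs no assumption.

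3. **Counting the cases.** Assume only that if no other cause can explain the event, an alternative cause is unlikely. That leaves three coherent (C, U) pairs: yes/yes, yes/no and no/yes. The total is 2 × 2 × 3 = 12 combinations.
   - Not related: 6 with T absent, plus 4 with T and C present, giving 10.
   - Related: T, K and U with C either way, giving 2.
   - Both: T, K, C and U, giving 1.
   - Neither: 12 − (10 + 2 − 1) = 1, the gap case.

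   These are logical cells and say nothing about how often each occurs.

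4. **Deleting the pattern clause and nothing else.** Related becomes T and U: 4 combinations. Neither: 0. Both: 2 (T, C and U, with K either way). Check: 10 + 4 − 2 = 12. The gap closes but the overlap grows from 1 to 2, so a tie-break is needed.

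5. **Default plus tie-break.** Let M mean that another cause is more likely than the study product to explain the event. Set Not related = (not T) or M, and Related = everything else. Over T, K and M there are 8 combinations: Not related 4 + 2 = 6, Related 2, both 0, neither 0.

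6. **Scale.** No rate of novel events is given, so the bias cannot be computed. It is zero if gap events are filed as Related and downward if they are filed as Not related. If incidence is counted per subject, and the subject has no other related TEAE, one misfiled subject changes a cohort of four (Section 4) by 1/4 = 25 percentage points and 16 subjects by 1/16 = 6.25.

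7. **What does not depend on the endpoint.**
   - All-cause TEAE incidence is reported beside it (Section 10.2.3).
   - Every SAE goes to the sponsor regardless of causality (Section 9.3.1).
   - Investigators must alert the sponsor to unusual events (Section 9).
   - The safety meeting weighs all AE information (Section 4).
   - The escalation stop in Section 15.4 uses the wider notion of possible relatedness.
   - The exception in Section 6.2.7 needs an unrelated event, and on the text of Section 9.1 a gap event is not one.

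**The case against.** The strongest reply is that a known response pattern can be read broadly. Section 9.1 does not limit it to human data or to the Investigator's Brochure, so pharmacology and animal findings may count. The grammar even allows it to mean a pattern of onset timing. Investigators will use judgement, and the endpoint is descriptive, in at most 16 subjects at one centre, with all-cause incidence alongside.

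The points on weight stand. The broad readings narrow the gap without closing it, because the pattern remains a required condition. Judgement does not help either, since the section says that its definitions are the ones to be used. A later analysis plan cannot easily recover a causality call made under them.

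Three stronger inferences are tempting, and the protocol does not support them.

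- *That gap events are likely here.* Section 15.4 says "Although not evident in human studies, preclinical animal data also suggest a potential for an increased QTc intervals" and mentions in vitro opioid-receptor effects. Because the protocol names these effects, an investigator may fairly treat them as known; they are boundary cases. Section 1 speaks of "a unique population that is quite disparate from that of previous trials", but there it is arguing that the discontinued lung cancer trial should not weigh against this one, and it says nothing about new toxicity.
- *That Section 9.1 contradicts the separate handling of expectedness.* Under Section 9.3.1 the sponsor "will assess the expectedness of each SAE in relation to the study treatment", and Section 9.5 says "SUSARs meets the same criteria as SARs, but are not expected to occur according to the reference safety informations", with the Brochure as reference. A reaction may fit known pharmacology and still be unlisted, so it can be Related and unexpected at once. The two ideas are close but not the same.
- *That subjects are left unprotected.* The safeguards listed in the working do not rest on the related-TEAE count.

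**Conclusion.** The point holds in a limited form. Section 9.1 cannot class an event with reasonable timing, no other explanation and no known pattern, and nothing else in the protocol supplies a default. The related-TEAE endpoint is undefined for such an event. It is understated only if investigators choose Not related, and by an amount that the protocol does not allow one to estimate. The gap itself rests on the wording alone. The cell counts rest on the one assumption stated with them, and the percentage points on per-subject counting. This is a defect in the definition of a descriptive secondary endpoint, worth correcting because correction is cheap. It is not evidence that the endpoint will be biased or that dose decisions are unsafe.

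**What to change.** In Section 9.1:

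- Add: *Any AE that does not meet Not related is classed as Related; a known response pattern supports but is not required for Related.*
- Change the second limb of Not related to: *another cause is more likely than the study product to explain the AE.*

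Every event then falls in exactly one class, provided that the unlikely-alternative wording in Related is read to match: no other cause is more likely than the product. An event for which the two are equally likely becomes Related. Deleting the pattern clause alone is not enough, because it enlarges the overlap. Expectedness stays with the sponsor, and the wider threshold in Section 15.4 should not be redefined through Section 9.1.

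The cost is one added sentence, one reworded limb and matching CRF guidance. The reported related-TEAE incidence may rise for two reasons: gap events now count, and so do events for which another cause is possible but not more likely than the drug.
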